Endogenous circadian rhythms of cardiovascular (CV) risk factors are rarely studied in obese humans. Thus, we aim to determine whether obese individuals have elevated morning CV risk because of normal CV rhythms on top of their existing increased CV risk (e.g., hypertension and increased sympathetic activation), or whether obesity disrupts CV rhythms and thereby furthers CV risk. Using an established multi-day circadian protocol in humans performed in dim light with behaviors scheduled evenly across the entire circadian cycle, our aims are to determine: (1) if obese individuals have normal or abnormal basal circadian CV rhythms, and (2) if obese individuals have normal or abnormal circadian rhythms in CV reactivity to stresses.

Specifically, we aim:

- a. To test if the circadian amplitudes and phases of important obesity-related CV risk markers are affected by obesity. We hypothesize that there will be endogenous circadian rhythms in CV risk markers including important hemodynamic variables (blood pressure, heart rate, vascular endothelial function), plus circulating markers of prothrombotic state, oxidative stress and inflammation in both obese and lean individuals. We expect the mean levels of these markers to be impaired in obese individuals along with changes in circadian rhythm amplitude contributing to increased CV risk during the morning period of CV vulnerability.
Sub aim a1: Determine in lean healthy humans if CMF, measured as coronary microvascular blood flux, has an endogenous circadian rhythm with lowest function in the morning.
i. Sub aim a2: Test the hypothesis that people with obesity have impaired coronary microvascular blood flux compared to lean individuals, with the exaggerated impairment during the morning.

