Obesity and cardiovascular risk. The prevalence of obesity in the US has increased dramatically over the last 25 years such that now over a third of adults are obese, and this is projected to reach 50% by 2030 (7-9). Obesity increases the risk for cardiovascular (CV) disease, the leading cause of death in both males and females (10-12). Increased body fat, in particular central adiposity, contributes substantially to circulating levels of leptin, tumor necrosis factor- α (TNF- α), interleukin-6 (IL-6) [leading to CRP release from the liver], plasminogen activator inhibitor-1 (PAI-1), and angiotensinogen leading to a relatively pro-thrombotic state with chronic inflammation, increased sympathetic nervous system (SNS) activation, hypertension (HTN) and obstructive sleep apnea (OSA) – all notable CV risk factors (13-18). There are also adaptations in cardiac structure and function with increased adiposity even in the absence of HTN or other pathological states (19,20). To meet increased metabolic needs with obesity, blood volume and cardiac output increase, leading to heart chamber enlargement, left ventricular hypertrophy, reduced diastolic compliance, increased left ventricular filling pressure and in some cases, heart failure. Obesity related systemic HTN combined with other cardiometabolic risk factors leads to coronary heart disease (19). Ultimately, there is a fivefold increased risk of death from CV disease in obese individuals (21,22).

Circadian pattern of adverse CV events. Overall, obesity increases the risk of adverse CV events including myocardial infarction (MI) (23,24), sudden cardiac death (SCD) (12,25,26), and stroke (27).

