Bristol Myers Squibb) will be used. One vial of Definity (1.3 mL) will be diluted to a total volume of 30 mL and infused at 1.5 ml/min intravenously. Myocardial contrast echocardiography will be performed with a phased-array transducer interfaced with an ultrasound system (iE33, Philips Ultrasound). A contrast-specific multipulse amplitude-modulation sequence will be performed at a centerline transmission frequency of 1.8 MHz, a mechanical index of 0.12, and a compression of 60. Images will be acquired in the apical 4-chamber, 2- chamber, and 3-chamber views. End-systolic images will be acquired for 10 seconds after a 5-frame destructive pulse sequence performed at a mechanical index of 1.0. Vasodilator stress will be applied using i.v. regadenoson and echocardiography will be repeated to measure the effect of hyperemia.

- j. **Exercise Test:** All team members have extensive experience in performing exercise testing under laboratory conditions. The power setting of the cycle ergometer will be tailored to induce 50% HR_{MAX} for each individual during their initial exercise test and kept constant for subsequent tests to enable us to quantify changes across the circadian cycle. This workload is similar to that in our preliminary data and chosen to reflect the type of workload placed on the CV system during normal daily activities (e.g. walking). This level elicits characteristic hemodynamic responses without causing an anaerobic state or training effects (48,49). The procedure is: (i) sit quietly on the ergometer for 5-10 min for baseline recordings; (ii) cycle for 15 min at 50% HRmax, and (iii) remain on the ergometer, stationary and resting for a 5-10 min recovery period.
- k. **Energy Expenditure:** We will measure energy expenditure via indirect calorimetry for assessment of EE and macronutrient oxidation (calculated using equations of (Jequier, 1987) during different portions of the inpatient protocol. O2 consumption and CO2 production are used to calculate metabolic rate and the oxidation of carbohydrate and fat (50).

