Analysis of myocardial perfusion imaging. Image analysis will be conducted offline. The immediate post-destruction frame will be digitally subtracted from all subsequent frames. Time versus background subtracted intensity will be measured on the background-subtracted frames from regions-of-interest placed over the myocardium according to the American Society of Echocardiography's 17-segment model. Data will be fit to the function $y=A(1-e^{-\beta t})$ where y is the video intensity at time t ; A is plateau video intensity, an index of capillary blood volume and β is the rate constant which provides a measure of average erythrocyte flux rate. Microvascular blood flow will be calculated by the product of A and β . Since flow reserve and β -reserve can be abnormal from increased resting values more so than reduced stress values, the definition of microvascular dysfunction will also require that complete refill of the microcirculation take >2 postdestructive beats. These data will be further analyzed using mixed model analysis with β -reserve as the primary dependent variable and circadian time as the independent variable.

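### For sub aims a1 and a2, the primary β-reserve analysis cannot by itself tell low stress flux from high resting flux, and the plan's refill safeguard does not reach it

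*Combined protocol and SAP*

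**What the plan says.** The aims state sub aims a1 and a2 in terms of flux. Sub aim a1 asks "if CMF, measured as coronary microvascular blood flux, has an endogenous circadian rhythm", expected to be lowest in the morning. Sub aim a2 expects lower flux in obesity, more so in the morning.

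Section 6i obtains both components: after the resting images, "Vasodilator stress will be applied using i.v. regadenoson and echocardiography will be repeated to measure the effect of hyperemia".

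Section 8 (Analysis of myocardial perfusion imaging) fits a refill curve with plateau A and rate constant β, where β "is the rate constant which provides a measure of average erythrocyte flux rate". It computes flow as A×β. It then warns that flow reserve and β-reserve "can be abnormal from increased resting values more so than reduced stress values" and so adds that "the definition of microvascular dysfunction will also require that complete refill of the microcirculation take >2 postdestructive beats". The next sentence gives the analysis: "mixed model analysis with β -reserve as the primary dependent variable and circadian time as the independent variable". No model is specified for resting β or stress β taken separately.

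**The concern.** The plan names a weakness of reserve and protects a classification against it, then makes the unprotected continuous variable the primary one. The refill criterion is not a term in the mixed model and does not change any value of β-reserve.

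Sub aims a1 and a2 predict a lower measure in obesity, lowest in the morning. In β-reserve, that pattern could come from reduced hyperemic flux, which is impairment, or from higher resting flux with a normal hyperemic response. The Background makes the second route conceivable. In section 3, "To meet increased metabolic needs with obesity, blood volume and cardiac output increase", and heart rate and sympathetic activation are listed among factors that surge around the morning. If the model is read as written, with no rule tying reserve to its components, raised resting flux could be reported as the hypothesised impairment. A real, proportional fall in both states could go unseen.

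**Working it through.** **Definition.** The documents do not write out β-reserve. Their contrast of resting with stress values, and the repeat imaging under regadenoson, imply reserve = S / R, with S = stress β and R = resting β. That reading is used here.

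**Step 1: raise R and hold S fixed.** If R becomes R(1 + x), reserve changes by 1/(1 + x) − 1, whatever its starting value:

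- x = 10%: 1/1.1 − 1 = −9.1%
- x = 20%: 1/1.2 − 1 = −16.7%
- x = 30%: 1/1.3 − 1 = −23.1%

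**Step 2: lower both equally.** If S and R are both multiplied by k, (kS)/(kR) = S/R. A uniform fall in flux leaves reserve unchanged.

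**Step 3: the plan's own figure.** Section 9 gives 10 lean and 10 obese participants with 80% power for these sub aims. It states no effect size, SD, alpha or sidedness for them, so the figure cannot be reproduced. Only the group size is used below.

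**Step 4: what the shift could do to a group comparison.** Every input except n = 10 per group is an assumption. Stress β is set equal in the two groups, there is one value per person, and the test is two-sided at 0.05.

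(a) Two-sample t-test, lean reserve 3.0. Reserve in obesity is 3.0/1.1 = 2.73, 3.0/1.2 = 2.50 and 3.0/1.3 = 2.31, so the differences are 0.27, 0.50 and 0.69. The chance of a significant difference, against a nominal 5%, is:

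| Between-person SD | rest +10% | rest +20% | rest +30% |
|---|---|---|---|
| 0.6 | 16% | 42% | 68% |
| 1.0 | 9% | 19% | 31% |

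(b) Simulation on log reserve (20,000 runs), with resting and stress β independent. Only significant results in the direction of lower reserve in obesity are counted; the rate with equal resting β is 2.4%:

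| CV of each component | rest +10% | rest +20% | rest +30% |
|---|---|---|---|
| 20% | 11% | 29% | 51% |
| 30% | 7% | 15% | 27% |

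The range is therefore 7 to 68%. It illustrates how sensitive the result is and does not predict what this trial will find. The test is also simpler than the plan's mixed model over up to three scans per person, and it says nothing about the size of a within-person morning effect.

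**Step 5: what the components add.** On the log scale, the difference in reserve equals the difference in stress β minus the difference in resting β. If the estimated reserve is lower and stress β is not, resting β must be higher. Fitting all three therefore shows where a change in reserve comes from.

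**The case against.** The strongest reply is that nothing needed to separate the two explanations is missing. Resting and regadenoson images are both planned, A and β are fitted, and calling one variable primary implies that others will be looked at. That stands: a reader might infer that the trial cannot distinguish impairment from raised resting flux, and the documents do not support this. The gap is in what is pre-specified.

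A reader might also infer that the documents show higher resting β in obesity and in the morning. They do not. Cardiac output is a whole-body quantity, the morning surge is described in healthy and generally lean people, and no resting or stress β values are given. The premise is plausible only.

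A third tempting step is to say that β-reserve is the wrong endpoint and should give way to hyperemic β. That is not established either. Reserve is a legitimate index: a smaller capacity to raise flow at a vulnerable time fits the protocol's interest in reactivity, even if high resting demand is the cause. Sub aim a1 does not say whether flux means rest or stress. Stress β may also vary more between people than a self-normalised ratio, which would bear on the 80% power claimed for 10 per group.

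What survives is that the refill criterion does not touch the continuous model, and no rule links β-reserve to its components.

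**Conclusion.** The concern holds as a point of pre-specification and interpretation for sub aims a1 and a2. As written, the primary model could present raised resting flux as microvascular impairment, or miss an equal proportional fall at rest and under stress. The arithmetic is firm given the stress-over-rest reading: 10, 20 or 30% higher resting β lowers reserve by 9, 17 or 23%. The chance of a misleading significant result is not known. The 7 to 68% range rests wholly on assumed resting differences, SDs and CVs, and on a two-group test the plan does not state.

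The scope is limited. Section 9 names systolic BP, heart rate and FMD as the main outcomes of interest, and a reader should not infer that those comparisons are affected.

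**What to change.** In section 8, Analysis of myocardial perfusion imaging:

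1. Keep β-reserve as the primary dependent variable, and write out its formula.
2. Pre-specify the same mixed model for stress (regadenoson) β and for resting β, with A×β alongside, and report estimates with confidence intervals next to those for β-reserve.
3. State that lower β-reserve will be interpreted as microvascular impairment only if stress β is also lower, and otherwise as raised resting flux.

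The change should be made before the perfusion data are analysed, since deciding afterwards which component to believe would be post hoc. It costs two further model fits and a stricter condition for claiming impairment. Both sets of images are already planned, so it needs no new scans or participants.

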- iii. **Specimen Handling:** Blood and urine samples will be identified only by the code assigned at the initial phone screen. Processing and handling of samples will be done by the OCTRI nursing and core lab staff. Samples will be stored and maintained by the OCTRI core lab -80 degree freezers. Access to study samples at OHSU will be limited to OCTRI core lab staff and study personnel listed on the IRB approved protocol. Coded biological samples may be sent to outside labs for analysis.

b. **Sharing of Results with Subjects**

With their consent, we will make known to the participant some of the information we have gathered from the physiological testing during screening and in the laboratory. There is a chance that the pre-study screening or the various blood and urine samples taken during the study will reveal some medical abnormality. This information will be conveyed to the participant, together with a recommendation to discuss the results with a physician if appropriate. Specifically, since genetic information obtained does not have medical or treatment importance at this time it will not be shared with the participant.

8. Data Analysis

Analysis of circadian rhythmicity: Forced desynchrony data is composed of circadian effects (intrinsic period ~24 h), evoked effects (5 h 20 min behavioral cycles) and 'noise'. The intrinsic period of the circadian pacemaker will be assessed with standard techniques as used for 20 years by the Principal Investigator (65,66). This intrinsic period, derived from melatonin, will be used to assign a circadian phase (from 0° to 360°) to each minute of the study, with 0° corresponding to the minimum of the waveform fitted to the DLMO data from the FD portion of the study. Analysis then proceeds in two ways. (A) Binning: Data for each variable and each participant will be 'binned' according to circadian phase and an average value per bin will be calculated. Data will then be averaged across participants. Bin size will be determined by the nature of the data being analyzed; in most cases we have found that a bin size of 60° (~4 h) allows sufficient detail while at the same time provides data for each participant in each bin. (B) Cosinor analysis to estimate rhythm amplitude and phase (67): Using regression techniques, time series data, not necessarily evenly spaced, can be fit to the function. This can be done within-subject, so standard deviations of amplitude and phase can be estimated (68).

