9. **Power / Sample Size Justification:** To estimate sample size, we have preliminary data from a similar study population (4 obese, 6 lean), in the same age range, and under the same protocol as the current proposal. The variables will be compared across circadian phases, across stresses, and between obese and lean groups in terms of basal circadian rhythm amplitudes (Aim 1) and circadian rhythms of reactivity (Aim 2). The main outcomes of interest are: differences in systolic BP, HR or vascular endothelial function (FMD) between obese and lean individuals upon awakening; changes in these variables with behavioral stresses, and between the most vulnerable (~9AM) and less vulnerable other circadian phases (e.g., 12 h later). The clinically significant or meaningful differences that we aimed to detect between groups, between states and between circadian phases were 10 mmHg for systolic BP, 10 bpm for HR and an absolute 3 point different in % FMD (73-76). The sample size calculations revealed that for all 6 main comparisons, 14 participants per group was sufficient to provide at least 80% power to identify the assumed main effects. To account for multiple comparisons, even after adjusting for six outcomes of primary interest (adjusted level of significance = 0.00833 per comparison), use of 14 participants for each of obese and lean groups, we have 80% power to detect effect sizes of at least 1.41 SD between groups. Thus, we will study 14 participants per group to adequately test our hypotheses. For our sub aims a1 and a2 related to circadian rhythmicity in coronary microvascular function between lean and obese individuals, in order to test the hypotheses with

80% statistical power, out of the total 28 participants, we will study 10 lean and 10 obese individuals.

Privacy, Confidentiality, and Data Security

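### The only model stated for the myocardial perfusion data has no group term and no group-by-circadian-time term, so as written it cannot estimate sub-aim a2

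*Combined protocol and SAP*

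**What the plan says.** The aims at the start of the protocol contain two perfusion sub-aims. Sub-aim a1 concerns lean participants only: "Determine in lean healthy humans if CMF, measured as coronary microvascular blood flux, has an endogenous circadian rhythm with lowest function in the morning". Sub-aim a2 is comparative: it hypothesises that "people with obesity have impaired coronary microvascular blood flux compared to lean individuals, with the exaggerated impairment during the morning".

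Section 8, Analysis of myocardial perfusion imaging, ends with the one inferential model for these data. It is a mixed model with β-reserve "as the primary dependent variable and circadian time as the independent variable". No other term is named.

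Two other places bear on the point.

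- **Section 8, Analysis of circadian rhythmicity**, gives general methods for all variables: binning by circadian phase with averaging across participants, and "Cosinor analysis to estimate rhythm amplitude and phase", which can be fitted within a participant. Neither names a group factor.
- **Section 9** says that variables will be "compared across circadian phases, across stresses, and between obese and lean groups in terms of basal circadian rhythm amplitudes (Aim 1"). For the sub-aims "related to circadian rhythmicity in coronary microvascular function between lean and obese individuals", it claims 80% power and says that "out of the total 28 participants, we will study 10 lean and 10 obese individuals". It names no model term, contrast, effect size, SD or alpha for β-reserve.

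Sections 4 (Cardiac ultrasound) and 6f make the perfusion scans optional, with at most three per participant.

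**The concern.** Sub-aim a2 has two parts: a difference between obese and lean participants, and a larger difference in the morning. The first needs a group term and the second a group-by-circadian-time term. The stated model has neither, so an analyst who followed it exactly would have no estimate, interval or test for a2, although section 9 claims 80% power for it.

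In practice the analyst would add something. The terms, the coding of phase and the meaning of morning would then be open to choice after the data are seen, with about 20 participants and few scans each. Different reasonable choices could give different answers.

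**Working it through.** **1. What the stated model returns.** Let *Y* be β-reserve for participant *i* at scan *j*, *u* a participant random intercept and *e* the residual (the plan does not name the random effect; an intercept is the simplest reading).

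- As written: *Y* = b0 + f(circadian time) + *u* + *e*. At any phase the fitted mean is the same for lean and obese participants. Any real group difference goes into *u*, and any difference in rhythm into *e*.
- What a2 needs, with G = 1 for obese and M = 1 for a morning scan: *Y* = b0 + bG·G + bM·M + bGM·G·M + *u* + *e*. The morning exaggeration is bGM. With one morning scan in three, the group effect averaged over scans is bG + bGM/3. The lean rhythm for a1 is bM.

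One simulated data set shows this (20 participants, 3 scans each; true group difference −1.3, true group-by-cosine term −0.4). The model as written returned only an intercept (−0.81), a cosine term (0.25) and a sine term (−0.06). With group terms added, the same data gave a group difference of −1.35 and a group-by-cosine term of −0.24.

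**2. Whether the general methods supply the missing test.** Take per-participant cosinor amplitudes from section 8 and compare them between groups, as section 9 suggests. A cosinor has three parameters (mean, amplitude, phase), so each participant needs three scans at distinct phases; a participant with one or two scans drops out. Amplitude also carries no timing. If both groups have amplitude A, with the lean trough in the morning and the obese trough 180° away, the morning deviation from the mean is −A in lean and +A in obese. The amplitude difference is zero, yet the morning contrast differs by 2A. An amplitude comparison therefore does not test a2's morning clause.

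**3. The plan's own power figure.** Section 9 states 1.41 SD detectable with 14 per group at 0.00833 and 80% power, for the main outcomes. For a two-sided two-sample t-test (df 26), the required noncentrality is 3.733, and 3.733 × √(2/14) = 1.411 SD. The figure reproduces. No such figure is given for β-reserve, so the 80% claim for a1 and a2 cannot be checked.

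**4. Size of what the added terms could detect.** From the plan: 10 + 10 participants, at most 3 scans, 80% power, and 0.00833 as the level used for the main outcomes. Assumed: one morning and two other scans each; single-scan SD = 1; ICC 0.3 to 0.7; two-sided 0.05 as the alternative level.

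- *Group-by-morning contrast.* The per-participant contrast (morning minus the mean of two others) has variance (1 − ICC)(1 + 1/2) = 1.5(1 − ICC). The group difference has SE √[1.5(1 − ICC) × 2/10] = √[0.3(1 − ICC)]. Residual df = 60 − 20 − 2 = 38; the required noncentrality is 2.875 at 0.05 and 3.648 at 0.00833.

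| ICC | SE | Detectable at 0.05 | Detectable at 0.00833 |
|---|---|---|---|
| 0.7 | 0.300 | 0.86 | 1.09 |
| 0.5 | 0.387 | 1.11 | 1.41 |
| 0.3 | 0.458 | 1.32 | 1.67 |

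- *Group difference.* With df 18, 2.963 × √(2/10) = 1.32 SD of a per-participant summary at 0.05, and 3.859 × √(2/10) = 1.73 at 0.00833.
- *a1 in 10 lean participants.* SE √[0.15(1 − ICC)], df 30 − 10 − 1 = 19, noncentrality 2.954: 0.63 to 0.96 single-scan SD at 0.05 (ICC 0.7 to 0.3).
- *Two scans each (one morning, one other).* The contrast variance is 2(1 − ICC), so the SE is √[0.4(1 − ICC)], with df 40 − 20 − 2 = 18. The detectable group-by-morning contrast is 1.03 to 1.57 SD at 0.05 (ICC 0.7 to 0.3).

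**The case against.** The strongest reply is that the sentence in section 8 is shorthand. Sub-aim a2 and section 9 leave no doubt that obese and lean participants are to be compared, and a competent statistician would add group. That stands as a statement of intent. It does not say which terms, how phase is coded or what morning means.

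A second reply is that the general methods already supply a route: fit a cosinor to each participant and compare amplitudes between groups. A reader might infer that three scans rule this out because three parameters leave no residual degrees of freedom. That goes too far. Zero residual degrees of freedom removes the within-participant standard error, not the estimates; a second-stage comparison of 10 with 10 takes its error from the spread between participants (df 18). The route is available when all three scans exist. What it lacks is a test of the morning clause, and any use of participants with fewer scans.

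A reader might also infer that the plan will pool both groups and mistake a dip in obese participants for a lean rhythm. The documents do not support that: a1 is worded for lean people, and the stated model is adequate for a1 if fitted in them. The plan does not say to restrict the fit, but neither does it say to pool.

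Nor can one infer that the 80% power claim for the sub-aims is false. Its inputs are not given, so it can be neither confirmed nor refuted.

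Finally, section 9 names systolic blood pressure, heart rate and flow-mediated dilation as the main outcomes. Perfusion imaging is optional and covers 20 of 28 participants. This limits the weight of the point.

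**Conclusion.** The concern holds. Followed as written, the only model stated for β-reserve gives no estimate of the obese–lean difference or of its morning exaggeration, which are the whole content of sub-aim a2. This follows from reading the aims against section 8 and rests on no assumption. The rest of the plan shows that the comparison is intended, but supplies at most an amplitude comparison that does not address the morning.

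The detectable sizes are illustrations only. They depend on the assumed ICC, scan pattern and alpha. Across those ranges the group-by-morning contrast detectable with 80% power runs from 0.86 to 1.67 single-scan SD, so moderate differences would probably be missed even with the right model.

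The point should be fixed before the perfusion data are analysed. It does not touch the main outcomes.

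**What to change.** In section 8, Analysis of myocardial perfusion imaging, replace the single-variable model with a mixed model of β-reserve that has fixed effects for group, circadian phase and group-by-phase, and a participant random intercept. Then state:

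- **a1:** the circadian phase effect (morning versus other phases) within lean participants.
- **a2:** the group effect, and one prespecified group-by-morning contrast.
- **Morning:** a window in circadian degrees on the melatonin-based scale that section 8 already defines. Section 9 names about 9 AM as the most vulnerable phase for other outcomes, which gives a starting point.

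The cost is a few model terms and no extra imaging. The price in inference is that the group-by-morning test will be imprecise with 10 + 10, and more so if participants have fewer than three scans.

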To determine the effects of obesity and specifically abdominal fat on our outcomes of interest, we will compare 2 groups of participants, ages 25-65: (1) healthy obese [$30 \leq \text{BMI} < 40 \text{ kg/m}^2$] and (2) healthy lean controls [$18.5 < \text{BMI} < 25 \text{ kg/m}^2$]; n=14 in each group. To ensure some degree of stability and avoid recent changes due to significant recent weight gain, all obese participants must report the presence of obesity with abdominal adiposity for >5 years. Participants must also be free of medication use. Based on experience in these protocols, we estimate that we will medically screen 120 participants in order to complete 28 participants.

b. Inclusion and Exclusion Criteria

In order to control for additional variation among obese individuals such as worse sleep at night or reduced daytime activity we will screen and match for insomnia, sleep apnea and overall habitual activity among our participants. Thus, we will exclude participants with moderate to severe obstructive sleep apnea based on an overnight sleep screen (Watch-PAT, Itamar Medical, Israel), we will exclude subjects with clinically significant insomnia (sleep efficiency less than desired, and residual daytime sleepiness based on the PROMIS Sleep Disturbance and Sleep-Related Impairment surveys).. The healthy control group will also be matched for age (+/- 5 years) and sex.

Diabetes. For participants who have a fasting blood glucose level of $\geq 100 \text{ mg/dL}$ we will measure hemoglobin A1c to exclude for diabetes ($\text{HbA1c} > 6.5\%$).

Hypertension. An upper cut off of 160/100 mmHg during an office BP measure will be used as an exclusion criterion as it would not be advisable to delay initiation of therapy in patients with severe hypertension.

Cardiovascular disease. Individuals actively treated or previously hospitalized for heart failure, arrhythmia or coronary artery disease, a history of coronary artery bypass grafts and coronary stents, and those that use a pacemaker or defibrillator will be excluded.

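### The six primary comparisons have only a fixed 0.05/6 level, stated in the sample-size section; naming Holm's procedure in the analysis section would add power at no cost in error control

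*Combined protocol and SAP*

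**What the plan says.** Section 9 (Power / Sample Size Justification) is the only place in the combined protocol and SAP that deals with multiplicity. It first reports that 14 per group gives at least 80% power for each of six main comparisons. The target differences are "10 mmHg for systolic BP, 10 bpm for HR and an absolute 3 point different in % FMD". It then repeats the assessment "even after adjusting for six outcomes of primary interest", at an "adjusted level of significance = 0.00833 per comparison". With "use of 14 participants for each of obese and lean groups", it concludes that "we have 80% power to detect effect sizes of at least 1.41 SD between groups".

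Section 9 does not list the six comparisons one by one. It describes three variables (systolic BP, heart rate and FMD), with contrasts between groups, across stresses and across circadian phases.

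Section 8 (Data Analysis) describes binning by circadian phase, cosinor fits, and a mixed model for the perfusion data. It gives no multiplicity rule for the final tests. Neither Bonferroni nor any stepwise method is named anywhere.

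**The concern.** A single level of 0.05/6 for each of six tests is a one-step Bonferroni split. Under that rule, once one comparison succeeds, the others still face 0.00833. Holm's procedure orders the p-values and tests the smallest at 0.05/6, the next at 0.05/5, and so on up to 0.05, stopping at the first failure. It holds the family-wise error at 5% under any dependence between the tests, and it rejects everything the fixed rule rejects and sometimes more.

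This matters because power is hard to buy here. Section 5a says of recruitment that "we estimate that we will medically screen 120 participants in order to complete 28 participants", and each participant completes a 5-day inpatient protocol. Section 2 hypothesises several differences (impaired mean levels, altered rhythm amplitude and exaggerated stress responses in obesity). Several real effects is the situation in which a stepwise rule helps.

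**Working it through.** **Inputs from section 9:** six comparisons; 0.00833 per comparison; 14 per group; 80% power; 1.41 SD. Sidedness is not stated. The SDs behind the raw target differences are not given, so the check is in SD units.

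**Step 1. The level.** 0.05 / 6 = 0.008333, which matches 0.00833.

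**Step 2. The power figure.** For a two-sample t-test with n = 14 per group:
- degrees of freedom = 2 × 14 − 2 = 26
- noncentrality = d × √(n/2) = 1.41 × √7 = 3.731
- two-sided critical value at 0.00833 = 2.856
- power = P(noncentral t > 2.856) = 79.9%

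The effect detectable at exactly 80% power is 1.411 SD. The stated 1.41 SD and 80% are therefore reproduced. Other readings do not match: the normal approximation gives 1.32 SD, a one-sided t-test 1.30 SD, and an unadjusted two-sided 0.05 gives 1.10 SD. I therefore take the tests as two-sided.

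**Step 3. Holm's levels.** The same t-test calculation at each step:

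| Step | Level | Power at 1.41 SD | Effect detectable at 80% power |
|---|---|---|---|
| 1 | 0.05/6 = 0.00833 | 79.9% | 1.41 SD |
| 2 | 0.05/5 = 0.0100 | 82.0% | 1.38 SD |
| 3 | 0.05/4 = 0.0125 | 84.3% | 1.34 SD |
| 4 | 0.05/3 = 0.0167 | 87.0% | 1.30 SD |
| 5 | 0.05/2 = 0.025 | 90.4% | 1.23 SD |
| 6 | 0.05/1 = 0.05 | 94.8% | 1.10 SD |

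The first step equals the plan's own level, so 80% power at 1.41 SD remains the minimum under Holm.

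**Step 4. Average power per real effect.** This was simulated with six two-sided t-tests and 14 per group. Three things are assumptions, because the documents do not give them: the number of real effects, a common effect size, and a common correlation of 0 to 0.5. All six are treated as between-group tests.

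| Real effects | 1.41 SD: fixed level → Holm | 1.0 SD: fixed level → Holm |
|---|---|---|
| 1 | 80% → 80% | about 43% → 43–44% |
| 2 | 80% → 81–82% | about 43% → 44–45% |
| 3 | 80% → 83–84% | 43–44% → 46% |
| 6 | 80% → 90–92% | about 43% → 53–54% |

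**Step 5. What does not change.** The chance of at least one rejection is identical under the two rules in every scenario, because the first step is the same. For example, at 1.41 SD with three real effects it is 99.2% under both rules at correlation 0, and 95.7% under both at correlation 0.5. Simulated family-wise error under Holm was at most 4.9%.

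**The case against.** The strongest reply is that the plan contains no error and that the fixed level is not clearly an analysis rule at all. The figure of 0.00833 appears once, as a check that 14 per group survives a correction for six outcomes. The same power statement would serve as the worst case for a Holm analysis. This largely stands. A reader might infer that the plan binds every final test to 0.00833. That is the natural reading, since no other rule is given, but section 8 does not say it. What can be said is conditional: if the fixed level governs, it wastes power; if it does not, the final tests have no stated rule.

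A second reply is that the large gains are a best case. This also stands. The rise to 90–92% needs all six effects to be real and each as large as 1.41 SD. Section 9 gives 1.41 SD as a detectable size, not as the expected truth, and sets no aim of succeeding on all six. With one to three real effects the gain is about 0 to 4 points.

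A third reply is that the simulated tests may not be the planned ones. Some contrasts in section 9 (across stresses and across phases) are within-subject, and no SDs are given for them. This limits the size of the gain that can be claimed. It does not affect the fact that Holm never rejects less.

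Two further inferences are tempting and unsupported. Correlation among the haemodynamic outcomes is not an argument for Holm, which makes no use of it; with six real effects its average power falls from 92% to 90% as correlation rises from 0 to 0.5. Nor does Holm justify a smaller sample, because its first step is the plan's own level.

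**Conclusion.** The concern holds as a low-cost efficiency improvement combined with a gap in section 8. The 0.00833 level, the 1.41 SD and the 80% power are all correct. A reader might conclude that the multiplicity adjustment is invalid or the sample size wrong; the documents support neither, since a 0.05/6 split controls family-wise error and the power figure reproduces.

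If the fixed level is used for the final tests, power is given up with no gain in error control. At 1.41 SD the loss ranges from nothing (one real effect) to 10–12 points per comparison (all six real: 90 − 80 and 92 − 80). At 1.0 SD with all six real it is about 10 points. These sizes rest on the assumed number of real effects, equal effect sizes, correlation of 0 to 0.5 and between-group tests throughout. Holm's advantage in principle rests on none of these.

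**What to change.** In section 8, list the six primary comparisons one by one, giving the variable, the contrast and the test for each. State that they will be tested with Holm's step-down procedure at a two-sided family-wise level of 5% (0.05/6, 0.05/5, 0.05/4, 0.05/3, 0.05/2, 0.05). In section 9, keep 80% power at 1.41 SD and describe it as the minimum, because it corresponds to Holm's first step.

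The Holm statement itself takes one sentence. The list takes more thought, but the fixed level needs it just as much. Both should be settled before the data are analysed. No change to the sample size or the measurements follows. The one drawback is that simultaneous confidence intervals are less direct under Holm; Bonferroni intervals can still be reported alongside the tests.
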